5.2 Trial Treatment(s)

The treatments to be used in this trial are outlined below in [Table 11](#).

Table 11 Trial Treatment

Drug	Weight	Dose/Potency	Dose Frequency	Route of Administration	Regimen/Treatment Period	Use
MK-5172A (fixed dose combination of EBR/GZR)	NA	50 mg/ 100 mg	QD	Oral	Arm 1: 8 weeks Arm 2: 12 weeks	Experimental

The first dose of trial treatment will be administered at the trial site at Visit 2 (Day 1). All other dosing will be performed by the subject (i.e., unsupervised at his/her home) at approximately the same time each day.

The investigator shall take responsibility for and shall take all steps to maintain appropriate records and ensure appropriate supply, storage, handling, distribution and usage of trial treatments in accordance with the protocol and any applicable laws and regulations.

5.2.1 Dose Selection/Modification

5.2.1.1 Dose Selection (Preparation)

The rationale for selection of doses to be used in this trial is provided in Section 4.0 – Background & Rationale. There are no specific calculations or evaluations required to be performed in order to administer the proper dose of EBR/GZR to each subject.

5.2.1.2 Dose Modification (Escalation/Titration/Other)

Dose modification of EBR/GZR is not permitted.

5.2.2 Timing of Dose Administration

EBR/GZR

Subjects will be instructed to take EBR/GZR without regard to food.

If a subject misses a dose of EBR/GZR and it is less than 8 hours before the next dose, the missed dose should be skipped and the normal dosing schedule resumed. Subjects should not double the next dose in order to compensate for what has been missed.

If for any reason EBR/GZR needs to be interrupted, it can be interrupted for up to 3 consecutive days. If the interruption lasts for more than 3 consecutive days, consult the Sponsor Protocol team.

5.2.3 Trial Blinding

This is an open-label trial; therefore, the Sponsor, investigator and subject will know the treatment administered.

5.3 Randomization or Treatment Allocation

In this open-label, partially randomized study, approximately 120 subjects will be enrolled. Approximately 75 (minimum of 60) TN subjects with stage 0-2 fibrosis will be randomized 2:1 to Arms 1 and 2, respectively. A total of approximately 45 TN subjects with stage 3-4 fibrosis and TE subjects with stage 0-4 fibrosis will be assigned (not randomized) to Arm 2. The treatment allocation ([Table 1](#)) will be implemented centrally using an interactive voice response system/integrated web response system (IVRS/IWRS).

5.4 Stratification

The randomized subjects will be stratified by baseline HCV RNA viral load: less than or equal to 800,000 IU/mL and greater than 800,000 IU/mL.

5.5 Concomitant Medications/Vaccinations (Allowed & Prohibited)

Medications or vaccinations specifically prohibited in the exclusion criteria are not allowed during the ongoing trial. If there is a clinical indication for any medication or vaccination specifically prohibited during the trial, discontinuation from trial therapy or vaccination may be required. The investigator should discuss any questions regarding this with the Sponsor Clinical Director. The final decision on any supportive therapy or vaccination rests with the investigator and/or the subject's primary physician. However, the decision to continue the subject on trial therapy or vaccination schedule requires the mutual agreement of the investigator, the Sponsor and the subject.

It is important for investigators to review each medication (prescription and non-prescription) the subject is taking before starting the study and at each study visit.

- At each visit, subjects should be questioned about any new drug they are taking
- To minimize the risk of adverse drug interactions, every effort should be made to limit the number of concomitant drugs to those that are truly essential.

- Drugs known to be hepatotoxic (i.e., drugs with a warning of hepatotoxicity in the package insert) should be avoided during the dosing period. Investigators are encouraged to review each medication for potential hepatotoxicity by searching the www.livertox.nih.gov website.

Listed below are specific restrictions for concomitant therapy or vaccination during the course of the trial.

The following medications/therapies are prohibited during the dosing period and for 14 days before and after the dosing period:

Known hepatotoxic drugs, including but not limited to:

- Etifoxine
- Isoniazid
- Nitrofurantoin
- Phenytoin
- Oral Ketoconazole

Strong and moderate CYP3A/P-gp inducers, including but not limited to:

- antibiotics: nafcillin
- antimycobacterials: rifampin
- anticonvulsants: carbamazepine, phenytoin
- endothelin Antagonists: bosentan
- Herbal Products: St. John's wort
- HIV Medications: efavirenz, etravirine
- Wakefulness-Promoting Agents: modafinil

OATP inhibitors, including but not limited to:

- immunosuppressants: cyclosporine
- antimycobacterials: rifampin
- HIV Medications: atazanavir, darunavir, lopinavir, saquinavir, tipranavir

HIV medications:

- Cobicistat-containing regimens - elvitegravir/ cobicistat/emtricitabine/ tenofovir (disoproxil fumarate or alafenamide)
- atazanavir,
- darunavir
- lopinavir
- saquinavir

- tipranavir
- efavirenz
- etravirine

HMG-CoA reductase inhibitors (statins):

- atorvastatin greater than 20 mg (see Allowed Medications, below)
- rosuvastatin greater than 10 mg (see Allowed Medications, below)
- fluvastatin, lovastatin, simvastatin (see Allowed Medications, below): The dose of fluvastatin, lovastatin, or simvastatin should not exceed a daily dose of 20 mg when co-administered with ZEPATIER. Statin-associated adverse events such as myopathy should be closely monitored.

The following medications/therapies may require dose adjustment or monitoring during the dosing period and for 14 days before and after the dosing period:

Co-administration with systemic tacrolimus increases the concentrations of tacrolimus. Therefore, frequent monitoring of tacrolimus whole blood concentrations, changes in renal function, and tacrolimus-associated adverse events upon the initiation of co-administration is recommended.

Other CYP3A4 substrates with narrow therapeutic ranges (e.g., alfentanil, astemizole, cisapride, dihydroergotamine, ergotamine, fentanyl, pimozide, quinidine, terfenadine) are not prohibited, but their concentrations have the potential to be increased by approximately 30-40%. Therefore, subjects taking these medications should be monitored closely or dose adjusted appropriately.

In general, P-gp substrates with narrow therapeutic ranges (e.g., digoxin and colchicine) are not prohibited, but their levels have the potential to be increased. Therefore, subjects taking these medications should be monitored closely.

Investigational agents are not permitted.

Systemic corticosteroids (dose equivalent to ≥ 10 mg prednisone per day, except in the case of rapid steroid tapers<1 week in duration) are not permitted.

Concomitant medications and therapies discontinued or dose adjusted during the dosing period may be restarted 2 weeks after the last dose of study drug is administered and may continue during the follow-up period.

The following medications/therapies are allowed in this study:

Antihypertensives:

- Angiotension-converting enzyme (ACE) inhibitors/angiotensin receptor blockers (ARB): enalapril, captopril, lisinopril, ramipril, valsartan, losartan, telmisartan
- Beta blockers: atenolol, metoprolol, propranolol

Note: for other beta blockers, please consult with the Sponsor

- Calcium-channel blockers: verapamil, diltiazem, amlodipine

Note: for other calcium-channel blockers, please consult with the Sponsor

- hydralazine, clonidine, minoxidil, isosorbide nitrates

Anemia: erythropoietin

Anticoagulants: warfarin, heparin, low molecular weight heparin, aspirin, fondaparinux, desirudin, acenocoumarol

Diuretics: HCTZ, furosemide, spironolactone, triamterene

Hypoglycemic agents: insulin, sitagliptin, glipizide, metformin

Contraceptives: oral contraceptive pills, progesterone injects, intrauterine devices

Antidepressants/anxiolytics: citalopram, paroxetine, duloxetine, escitalopram, fluoxetine, bupropion, trazodone, diazepam, clonazepam, temazepam, lorazepam

Acid reflux: H2 blockers, proton pump inhibitors, antacids

HMG-CoA reductase inhibitors (statins):

- pravastatin and pitavastatin: may be coadministered without dose adjustment
- rosuvastatin: the dose of rosuvastatin should not exceed a daily dose of 10 mg
- atorvastatin: the dose of atorvastatin should not exceed the daily dose of 20 mg
- fluvastatin, lovastatin, simvastatin: The dose of fluvastatin, lovastatin, or simvastatin should not exceed a daily dose of 20 mg when co-administered with ZEPATIER.
- HIV/HBV medications: abacavir, dolutegravir, emtricitabine, entecavir, lamivudine, raltegravir, rilpivirine, tenofovir disoproxil fumarate

Immunosuppressants: prednisone, mycophenolate mofetil

Opiate substitution therapy: buprenorphine/naloxone, methadone

Antiarrhythmics: digoxin

Phosphate Binders

Note: For other medications not listed here, please consult with the Sponsor.

5.6 Rescue Medications & Supportive Care

No rescue or supportive medications are specified to be used in this trial.

5.7 Diet/Activity/Other Considerations

EBR/GZR can be taken with or without food.

Considerations for Study Visits

Procedure visits should be scheduled as close to the indicated study days and study weeks as possible. See the Trial Flow Chart (Section 6.0) for a complete listing of study procedures required at each visit.

Subjects should complete study therapy as defined by the length of the assigned treatment regimen. If dosing is missed or interrupted (see Section 5.2.2), the assigned study therapy regimens should still be completed.

5.8 Subject Withdrawal/Discontinuation Criteria

5.8.1 Discontinuation of Treatment

Discontinuation of treatment does not represent withdrawal from the trial.

As certain data on clinical events beyond treatment discontinuation may be important to the study, they must be collected through the subject's last scheduled follow-up, even if the subject has discontinued treatment. Therefore, all subjects who discontinue trial treatment prior to completion of the treatment will still continue to participate in the trial as specified in Section 6.0 - Trial Flow Chart and Section 7.1.5 – Trial Procedures.

Subjects may discontinue treatment at any time for any reason or be dropped from treatment at the discretion of the investigator should any untoward effect occur. In addition, a subject may be discontinued from treatment by the investigator or the Sponsor if treatment is inappropriate, the trial plan is violated, or for administrative and/or other safety reasons. Specific details regarding procedures to be performed at treatment discontinuation are provided in Section 7.1.4 – Other Procedures.

A subject must be discontinued from treatment but continue to be monitored in the trial for any of the following reasons:

- The subject or legal representative (such as parent or legal representative) withdraws consent.
- Subject meets any HCV virologic failure criteria (see **Section 4.2.3.1.1.2**).
- Subject becomes pregnant during the trial.
- The investigator feels that it is in the best interest of the subject to discontinue.
- The subject's ALT or AST increases to >500 IU/L and is confirmed with repeat test within one week.
- The subject's ALT or AST increases to $>3x$ the nadir value, is $>3x$ ULN (confirmed with repeat test within one week), and there is a simultaneous increase in total bilirubin $>2x$ ULN and/or INR is increased from the baseline value and is >1.5 (unless the subject is on anticoagulation).
- The subject's ALT or AST increases to $>3x$ nadir, is $>3x$ ULN (confirmed with repeat test within one week), and is temporally associated with signs or symptoms of liver inflammation that are of moderate or severe intensity and deemed by the investigator to be at least possibly related to study therapy.

Clinical management of HIV-1 virologic failure will be handled by site investigators according to current HIV treatment guidelines and local standard of care. Subjects with HIV virologic failure may continue in the trial unless treatment with a prohibited concomitant medication (see Section 5.5) is required to construct a new HIV treatment regimen.

For subjects who are discontinued from treatment but continue to be monitored in the trial, see Section 6.0 - Trial Flow Chart and Section 7.1.5 – Trial Procedures for those procedures to be completed at each specified visit.

Subjects may be allowed to begin treatment again if deemed medically appropriate.

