5.8.2 Withdrawal from the Trial

Subjects may withdraw from the trial at any time for any reason. If a subject withdraws from the trial, they will no longer receive treatment or be followed at scheduled protocol visits.

A subject must be withdrawn from the trial if:

- The subject or legal representative (such as parent or legal representative) withdraws consent from the trial.
- The subject is lost to follow-up

Specific details regarding procedures to be performed at the time of withdrawal from the trial including specific details regarding withdrawal from Future Biomedical Research are outlined in Section 7.1.4 – Other Procedures.

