5.9 Subject Replacement Strategy

A subject who discontinues from the trial will not be replaced.

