7.1.5.4 Drug Administration

Following completion of the Day 1 procedures and confirmation of eligibility, the site pharmacist or study coordinator will contact the IVRS for assignment of the drug regimen to be administered and duration of treatment. Sites should not call IVRS for drug administration until the subject has met all criteria for the study and are ready to receive the first dose of study medication on Day 1.

The first dose of prescribed study medications should be administered at the Day 1 visit.

Subjects who discontinue therapy in the trial prior to the last scheduled treatment visit should have an Early Discontinuation visit and then continue into follow-up visits.

At a minimum, collect the following information when a subject discontinues:

- The reason the subject discontinued
- The date of the last dose of study medications from the trial
- The date of the last assessment and/or contact. A follow-up contact (telephone or visit) will be arranged as appropriate
- (Serious) Adverse events

Final Assessments:

- Every effort should be made to ensure that all procedures and evaluations scheduled for the Early Discontinuation Visit are performed.
- Retrieve all study medications from the subject.

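### Section 5.8.1 makes staying in the trial, rather than staying on EBR/GZR, depend on an HIV-failure subject not needing a Section 5.5 drug; read literally, this conflicts with the follow-up rules

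*Combined protocol and SAP*

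**What the plan says.** The sentence stands near the end of Section 5.8.1, Discontinuation of Treatment: "Subjects with HIV virologic failure may continue in the trial unless treatment with a prohibited concomitant medication (see Section 5.5) is required" to build a new HIV regimen. The paragraph after it begins "For subjects who are discontinued from treatment but continue to be monitored in the trial" and points to the flow chart and Section 7.1.5.

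Other parts of the protocol cover the same situation:

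- Section 5.5, on needing a prohibited medication during the trial: "discontinuation from trial therapy or vaccination may be required".
- The opening of Section 5.8.1 separates stopping treatment from leaving the trial, and adds that "all subjects who discontinue trial treatment prior to completion of the treatment will still continue to participate in the trial".
- Section 5.8.2 introduces its mandatory list with "A subject must be withdrawn from the trial if" and gives two entries: consent withdrawn from the trial, and loss to follow-up. A withdrawn subject has no further scheduled visits.
- Section 7.1.5.4: subjects who stop therapy early "should have an Early Discontinuation visit and then continue into follow-up visits".
- Section 7.1.5.5 places those visits at 4, 12 and 24 weeks after treatment is discontinued.
- Section 5.9: "A subject who discontinues from the trial will not be replaced".

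**The concern.** Sections 5.8.1 and 5.8.2 treat ending treatment and ending participation as different events with different consequences. The HIV sentence uses the term for the second where the first fits. It is also the only rule written for HIV virologic failure, so a site could take it as a specific exception to the general follow-up rule.

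At stake is the HCV RNA result on which SVR12 and SVR24 rest. A subject who stops EBR/GZR and stays in follow-up contributes an observed result, which may be a response or a failure. A subject taken out of the trial contributes none. In the FAS analysis of Section 8.6.1, any non-intermittent missing value is imputed as failure whatever the reason. Safety loses less: Section 7.1.4.1 still requires adverse events present at discontinuation to be followed, and Section 7.2.3.1 requires follow-up of serious ones to outcome.

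**Working it through.** The plan gives no figure on this point. The main check is a comparison of texts for one case: a subject who is still dosing, has HIV virologic failure, and needs an antiretroviral on the Section 5.5 prohibited list.

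1. What stops? Section 5.5 says trial therapy may have to. The HIV sentence, read literally, says participation does.
2. Does the subject stay in the trial after stopping? The opening of 5.8.1 says yes for all subjects who stop early, with no HIV exception. The HIV sentence, read literally, says no.
3. Is this a ground for mandatory withdrawal? Section 5.8.2 does not list it.
4. Which visits follow? Virologic failure in Section 7.1.5.5 is HCV failure, by its reference to Section 4.2.3.1.1.2. This subject therefore falls under discontinuation for other reasons: an Early Discontinuation Visit, then visits at 4, 12 and 24 weeks. Section 7.1.5.4 agrees.

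The literal reading disagrees at every step, and no text says which rule prevails.

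The scale can be illustrated with the plan's own method. For x responders among n, the rate is x/n. The Clopper-Pearson 95% limits are the 0.025 quantile of Beta(x, n − x + 1) and the 0.975 quantile of Beta(x + 1, n − x). This reproduces all 13 intervals in Table 17 to 0.1 point. Turning one responder into a failure lowers the rate by 1/n:

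| Group (target n) | Before | After | Loss |
|---|---|---|---|
| Arm 1 (50) | 49/50 = 98.0% (89.4, 99.9) | 48/50 = 96.0% (86.3, 99.5) | 1/50 = 2.0 points |
| Arm 2 (70) | 69/70 = 98.6% (92.3, 100.0) | 68/70 = 97.1% (90.1, 99.7) | 1/70 = 1.4 points |
| Arm 2, TN F0-F2 (25) | 24/25 = 96.0% (79.6, 99.9) | 23/25 = 92.0% (74.0, 99.0) | 1/25 = 4.0 points |

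The starting counts are hypothetical rows of Table 17. The third row matters only for the secondary objective in treatment-naïve F0-F2 subjects.

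In the supportive mFAS analysis, the result depends on how the reason for leaving is classed. If it is unrelated to treatment and no HCV failure is documented, the subject is excluded; in Arm 1 this gives 48/49 = 98.0% (89.1, 99.9), almost unchanged. If it is treatment related, the subject counts as a failure, as in the FAS. The plan does not say which class applies.

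**The case against.** The strongest reply is that the surrounding text already settles the meaning. The sentence sits under a heading about stopping treatment, the section opens by saying that stopping treatment is not withdrawal, and the next paragraph deals with subjects who are off treatment but still monitored. The HBV text in Section 7.1.3.4 uses the same phrase about continuing in the trial, which points to loose shorthand. This largely stands: the intent is fairly clear, and it is why the point is minor. It does not remove the conflict, because nothing subordinates the HIV sentence to the general rule.

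A reader might infer that the protocol orders HIV-failure subjects out of the trial. It does not. The sentence grants a permission with an exception, and no text tells a site to end follow-up. The conflict arises only from the literal reading.

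A reader might also extend the point to subjects who have finished dosing, because Section 5.5 says: "The following medications/therapies are prohibited during the dosing period and for 14 days before and after the dosing period". That is strained. It needs HIV failure, a new regimen and a prohibited drug all within the 14 days after dosing. It also needs a site to end follow-up, under a heading on stopping treatment, for someone with no treatment left to stop. Section 7.1.5.5 schedules follow-up after completed therapy in any case.

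Finally, the percentage-point losses are what losing any one responder would cost in groups of these sizes. That is correct; they are an illustration and not an estimate of what this sentence will do.

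**Conclusion.** The wording is wrong and should be corrected; severity is minor. For a subject still on dosing, the HIV sentence taken literally contradicts the rules that stop only EBR/GZR and keep the subject in follow-up.

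The consequence is conditional. A site must apply the sentence literally and remove the subject before FU12, and the subject must be one who would have reached SVR12 despite stopping early. The plan gives no probability for the last condition, so one responder per affected subject is a maximum.

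A reader might infer that the SVR12 estimates are threatened. The documents do not support that. HIV co-infected subjects may enter all arms (Section 4.2.1.5), but the number affected is not given and may be zero. Entry requires suppressed HIV RNA on a restricted list of antiretrovirals, or CD4+ above 500 cells/mm³ off therapy (Section 5.1.2), and Section 5.5 leaves several HIV drugs available. The flow chart schedules HIV RNA only at screening, so most HIV failures would probably come to light through local care.

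**What to change.** In the HIV sentence of Section 5.8.1, replace *may continue in the trial unless* with *may continue study treatment unless*. Then add: *Subjects who stop EBR/GZR for this reason continue in follow-up per Section 7.1.5.5 unless they withdraw consent from the trial.* The last clause preserves the right to withdraw under Section 5.8.2.

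The cost is one phrase and one sentence at the next amendment. No visits or procedures are added, because FU4, FU12 and FU24 are already scheduled, and the analysis rules stay as they are.

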5.8.2 Withdrawal from the Trial

Subjects may withdraw from the trial at any time for any reason. If a subject withdraws from the trial, they will no longer receive treatment or be followed at scheduled protocol visits.

A subject must be withdrawn from the trial if:

- The subject or legal representative (such as parent or legal representative) withdraws consent from the trial.
- The subject is lost to follow-up

Specific details regarding procedures to be performed at the time of withdrawal from the trial including specific details regarding withdrawal from Future Biomedical Research are outlined in Section 7.1.4 – Other Procedures.

5.9 Subject Replacement Strategy

A subject who discontinues from the trial will not be replaced.

5.10 Beginning and End of the Trial

The overall trial begins when the first subject signs the informed consent form. The overall trial ends when the last subject completes the last study-related phone-call or visit, discontinues from the trial or is lost to follow-up (i.e. the subject is unable to be contacted by the investigator).

5.11 Clinical Criteria for Early Trial Termination

There are no pre-specified criteria for terminating the trial early.

